8.6.4. Subgroup analyses

To explore the effect of treatment in subgroups, the estimated effect of the nutritional interventions will be estimated for each of the subgroups listed below will be derived. No adjustment for multiple comparisons will be made. Additionally, the frequency and percentage of subjects reaching the primary endpoint will be presented by treatment group for each of the subgroups based on the baseline measurements: baseline fat mass (\geq 20% and \geq 25% for men; \geq 30% and \geq 35% for women), age groups (30-50, 51-70 years), gender, baseline BMI (25-29.9; 30 and over);

8.7. Interim analysis

We will perform an interim analysis of the results obtained by participants enrolled who have completed the 6 months of treatment in order to determine the efficacy of the treatment to positively affect primary and/or secondary endpoints of the study. Statistical analysis will be performed as mentioned in section 8.6.1 and 8.6.2

9. Ethical Considerations

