2.2. Endpoints

- 2.2.1. *Primary endpoint*: maintenance of at least 50% of the fat mass lost during the previous trial and measured after one follow up year on FMD every 3 months
- 2.2.2. *Secondary endpoints*: maintenance of at least 50% of one or more risk factors improvements achieved during the previous clinical trial and measured after one year of follow up FMD cycles every 3 months including improvements in: body mass, body mass index, blood pressure, IGF-1, haemoglobin A1c, fasting glucose, LDL, total cholesterol, and C-Reactive Protein. Determine long-term trends in the reduction/stabilization in the use of antihypertensive and glucose-lowering drugs or other commonly used medications.

3. Study Design

Follow up clinical trial including participants of the approved studies “*Studio degli effetti della dieta mima-digiuno e della dieta della longevità sulla composizione corporea, fattori di rischio per malattie età-correlate e marcatori dell'invecchiamento in uno studio randomizzato*” and “*Studio degli effetti della dieta mima-digiuno e della dieta della longevità sulla composizione corporea, fattori di rischio per malattie età-correlate e marcatori dell'invecchiamento in uno studio randomizzato-2*” that will follow 5-day of the FMD meal program every three months, for one year.

Selection and withdrawal of subjects of the previous clinical study

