8.6.1. Analysis supporting primary objectives

Generalized mixed linear models will be used to compare the fat mass percentage change between the value measured at the end of the trial vs the baseline value. The analysis will include a fixed term modeling the change of fat mass between baseline and the second follow-up visit (after 1 year), as well as a random term accounting for repeated measurements on the

same participants. We hypothesize that the coefficient associated with the fixed term (fat mass) will be either equal to zero (no change) or negative (reduction of fat mass).

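### The 6-month interim analysis in Section 8.7 is meant to determine efficacy on endpoints defined only at one year, most of which have no 6-month data

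*Protocol*

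**What the plan says.** Section 2.2.1 defines the primary endpoint as "maintenance of at least 50% of the fat mass lost during the previous trial", and it is to be "measured after one follow up year on FMD every 3 months". Section 2.2.2 builds the secondary endpoints the same way, as "maintenance of at least 50% of one or more risk factors improvements achieved during the previous clinical trial", again after one year of follow-up cycles.

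Section 8.6.1 gives the primary analysis: a mixed model whose fixed term represents "the change of fat mass between baseline and the second follow-up visit (after 1 year"). The expected result is a coefficient of zero or below, so an unchanged fat mass counts as consistent with the hypothesis.

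Section 8.7 then sets an interim analysis in "participants enrolled who have completed the 6 months of treatment". Its stated purpose is "in order to determine the efficacy of the treatment to positively affect primary and/or secondary endpoints of the study", and the analyses are those of Sections 8.6.1 and 8.6.2. The section does not call the look descriptive and does not say what may be concluded from it.

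The visit schedule (Section 3.3, Table 1, and the text under Follow-up visit 1 and Follow-up visit 2) places bioimpedance, weight and vital signs at both 6 and 12 months. Follow-up blood sampling takes place at 12 months only.

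**The concern.** The study asks whether fat mass lost in the parent trial is still largely kept off a year later. A 6-month reading is an earlier and easier question. If Section 8.7 is followed as it stands, an analysis at 6 months carries the name of the primary endpoint and is given the task of determining efficacy. A favourable early result could then be presented as an answer to the 12-month question.

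There are two further consequences. Efficacy can be claimed on two occasions, on the primary endpoint, the secondary ones or both, and the text gives neither occasion priority. Also, a large part of the promised interim analysis cannot be carried out, because the blood results it needs are not collected at that visit.

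**Working it through.** No figure in the protocol needs reproducing for this point. The check sets the sections side by side and counts what is available at 6 months.

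**1. Time points.**

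| Item | Section | Time fixed |
|---|---|---|
| Primary endpoint | 2.2.1 | one year |
| Secondary endpoints | 2.2.2 | one year |
| Primary model contrast | 8.6.1 | baseline to second follow-up visit, one year |
| Interim analysis | 8.7 | 6 months of treatment |

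A participant who has reached only 6 months has no second follow-up value, so the Section 8.6.1 contrast cannot be formed for that person. Putting the 6-month value in its place gives a different quantity.

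**2. Why the two quantities are not interchangeable.** Write F_start and F_end for fat mass at the start and end of the parent trial, and F(t) for fat mass at month t of this study. The retained share of the loss is

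R(t) = (F_start − F(t)) / (F_start − F_end).

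The primary endpoint is R(12) ≥ 0.5. Section 2.2 does not define R(6) as an endpoint. As an illustration only, suppose there is no regain before this study's baseline and steady regain afterwards, with a share g of the loss regained by month 6. Then R(6) = 1 − g and R(12) = 1 − 2g. The 50% criterion is met at 6 months if g ≤ 0.5, but at 12 months only if g ≤ 0.25. Anyone with g above 0.25 and up to 0.5 passes at the interim and fails the actual endpoint. Steady regain is an assumption, since the protocol gives no trajectory.

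**3. Which listed variables have 6-month data.** Blood pressure is counted once and medication use is left aside.

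- Primary: fat mass. Measured at 6 months by bioimpedance.
- Secondary, measured at 6 months: body mass, BMI, blood pressure (3).
- Secondary, needing blood: IGF-1, HbA1c, fasting glucose, LDL, total cholesterol, CRP (6). Table 1 places haematological analyses at baseline and the second follow-up visit only, and the visit text agrees.

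So 1 + 3 = 4 of the 10 listed variables are available at 6 months, and 6 of the 9 named secondary variables are not. Medication use is unclear: the Follow-up visit 1 text includes current medications, but Table 1 does not tick them at that visit.

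**4. Section 8.6.2 at 6 months.** Its cut-offs are for total cholesterol, LDL, fasting glucose, triglycerides, CRP and IGF-1, all of which need blood. Its metabolic syndrome definition requires three of five conditions. Glucose, triglycerides and HDL need blood, which leaves 5 − 3 = 2 (abdominal obesity and blood pressure) observable at 6 months. The three-of-five definition therefore cannot be satisfied from data collected at that visit.

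**The case against.** **Table 1 ticks primary and secondary endpoint assessment at the 6-month visit.** It does, but it ticks the baseline visit too, where one-year maintenance cannot yet exist. The row can only mean that the underlying variables are recorded, and for the blood variables even that is not true at 6 months.

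**Interim levels and boundaries belong in a statistical analysis plan, which is not shown.** This is fair, and their absence is not held against the protocol. The point rests on what Section 8.7 does fix: an efficacy purpose, at a time that conflicts with Sections 2.2 and 8.6.1. A separate plan that followed Section 8.7 would inherit the conflict.

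**No efficacy stop is planned.** This is also correct. Sections 7.4.4 and 7.7 give safety, participants' interest and sponsor termination as the reasons to halt or discontinue. A second look affects the error rate only if it can lead to a claim or a change to the study. The words of Section 8.7 leave room for a claim but do not announce one.

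Four stronger readings are tempting, and the protocol does not support them:

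- *That the primary variable is missing at 6 months.* Fat mass is measured then. It is the endpoint that is undefined at that time.
- *That the false-positive rate rises by a definite amount.* No significance level, sidedness, interim sample size or study-level success rule is stated. The usual calculation for two looks, each two-sided, would also count a significant regain of fat as success, while Section 8.6.1 treats no change as a favourable result. A figure obtained by counting every listed endpoint would mostly reflect the multiplicity of the final analysis, which Section 8.7 does not cause.
- *That a very strict interim significance threshold would repair the section.* It would still permit an efficacy claim on a quantity that is not the endpoint.
- *That the 6-month result will be reported as the primary endpoint, or that seeing it will bias allocation.* Section 8.7 does not say how the result will be reported or who will see it. Under Section 3 all participants follow the same schedule, so there is no randomised allocation in this study to bias.

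**Conclusion.** The conflict stands on the protocol's own text. Section 8.7 asks for an efficacy determination at 6 months on endpoints, and with a model contrast, that are defined at one year. Four of the ten listed variables could be summarised at that visit. Six of the nine named secondary variables could not be analysed at all, and most of Section 8.6.2 could not be run.

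The section also opens a second opportunity for an efficacy claim. How much that matters for the error rate cannot be stated from this document and depends on rules it does not give. The time-point conflict does not depend on any assumed significance level, and it would remain even if there were no error inflation. It should be corrected before the interim analysis is carried out.

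**What to change.** Reword Section 8.7 along these lines:

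- The 6-month analysis is a descriptive summary of the change from baseline to 6 months in the variables measured at that visit (fat mass, weight, BMI and blood pressure), together with safety.
- These summaries are not called the primary or secondary endpoints, and no efficacy conclusion is drawn from them.
- The 12-month analysis is the only test of efficacy.
- The reference to running Sections 8.6.1 and 8.6.2 at the interim is removed, since the first is a one-year contrast and the second depends mainly on blood results not collected at 6 months.

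The cost is a few sentences in a protocol amendment and the loss of any early efficacy claim. No visit, sample or measurement changes.

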9.1. Declaration of Helsinki

The investigator will ensure that this study is conducted in full conformity with the current revision of the Declaration of Helsinki, or with the International Conference for Harmonization Good Clinical Practice regulations and guidelines, whichever affords the greater protection to the subject.

9.2. Informed Consent Process

Informed consent is a process that is initiated prior to the individual agreeing to screen for and participate in the study and continuing throughout the individual's study participation. Extensive discussion of risks and possible benefits of this therapy will be provided to the subjects. Consent forms describing in detail the Study Product, the study procedures and associated risks will be given to the Subject and written documentation of informed consent is required prior to screening for the previous study and if qualified, prior to starting the study. The subject will be asked to read and review the document. Upon reviewing the document, the investigator or designee will explain the research study to the Subject and answer any questions that may arise. The subjects will sign the informed consent document prior to any procedures being done specifically for the screening process and if qualified, for the study. The subjects will have sufficient opportunity to discuss the study and process the information in the consent process prior to agreeing to participate. The subjects may withdraw consent at any time throughout the course of the trial. A copy of all informed consent documents will be given to the subjects for their records.

The acquisition of informed consent will be documented in the subject's medical records. The informed consent form will be signed and personally dated by the subject and the person who conducted the informed consent discussion. The original signed informed consent form will be retained in the medical chart and a copy will be provided to the subject.

The study poses minimal risk for the participants. The anonymized information collected in the study will be used for research and publication purposes, and always safeguarding the right of privacy and anonymity according to the rules of General Data Protection Regulation (GDPR) of the European Union (UE) 2016/679.

This study will be initiated only after all required legal documentation has been reviewed and approved by the University of Palermo Ethic Committee, Comitato Etico Locale, CEL) according to the national and international regulations. The same applies for the implementations of changes introduced by amendments.

